1. OBJECTIVES

This is an open-label phase II study to evaluate the efficacy and safety of lenalidomide in participants with relapsed/refractory ECD or LCH and in any patient with HS requiring systemic therapy. Patients will receive up to 12 cycles of lenalidomide with treatment occurring on days 1-21 of each 28 day cycle. In cycle one patients will receive lenalidomide 10 mg daily due to the unknown incidence of tumor flare in this population (tumor flare has been observed in other diseases such as chronic lymphocytic leukemia). Patients who tolerate the 10 mg dose well will be escalated to 25 mg for future cycles. There will also be the possibility of dose reduction for patients who do not tolerate the 10 mg starting dose. Dosage thereafter will be adjusted based upon toxicity. Lenalidomide is known to increase the risk of venous and arterial thromboembolic events. Patients not already receiving systemic anticoagulation for other clinical indications will be required to take aspirin 325 mg daily for the duration of the protocol or for one month following treatment discontinuation, whichever is longer.

Disease assessments will occur at baseline and then again at cycle 3 day 1, cycle 6 day 1, cycle 9 day 1 and cycle 12 day 1 as well as every 3 months thereafter until month 24 from study initiation when disease assessment will occur every 6 months until month 36 from the initiation of treatment. Disease assessments will consist initially of an MRI of the brain/pituitary and PET/CT (although a CT of the chest, abdomen and pelvis along with a bone scan is allowed if PET/CT is rejected by insurance). Clinical documentation of skin lesions with photography is highly encouraged. Measurement and documentation of all skin lesions is required even if photography is not performed. A repeat MRI is not required beyond baseline if the MRI at baseline is normal and there is no clinical suspicion of CNS or pituitary involvement. A bone marrow biopsy is only required if the patient has at least one cytopenia of grade 2 or greater at baseline or has evidence of bone marrow involvement on PET/CT. The bone marrow biopsy only needs to be repeated if abnormal at baseline.

Patients will be followed for 3 years (thirty-six months) from the initiation of therapy or until they initiate a new therapy for their underlying disease, whichever occurs first.

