1.3 Secondary Objectives

- To define the progression free survival (PFS) after treatment with lenalidomide
- To define the overall survival (OS) after treatment with lenalidomide
- To describe the safety profile of lenalidomide in LCH, ECD, and HS
- To assess quantitative changes in urinary and plasma cell free DNA harboring the BRAF V600E mutation and correlate the presence or absence of the BRAF V600E mutation with response
- To assess serial changes in TNF-alpha levels in patients treated with lenalidomide
- To assess the mutational landscape of these diseases using Oncopanel

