steroid and cytotoxic regimens. Nucleoside analogues such as cladribine and cytarabine have proven to be effective in this setting but are not without issue. Cytarabine can have significant hematologic toxicity (9). Cladribine cannot be administered for longer than six months due to concerns about secondary myelodysplasia (MDS) while studies have suggested that outcomes are better when LCH is treated with a given agent for at least 12 months (10,11). Clofarabine has proven to be effective in patients with cladribine and cytarabine-resistant disease, but causes significant hematologic and hepatic toxicity as well as cause hand-foot syndrome (12). The BRAF inhibitor vemurafenib can be effective in cases of LCH that harbor the BRAF mutation but there are significant concerns about the potential for secondary skin cancers (13). Monitoring of BRAF mutational burden in cell free DNA may be a useful marker for disease progession in this patient population, however (14).

Histiocytic sarcoma is an aggressive neoplasm deriving from non-Langerhans dendritic cells. When localized, surgery and/or radiation can be effective. However, disseminated HS responds poorly to chemotherapy and is typically fatal within six months (15). Therefore, new therapies are required for all patients with multifocal HS and for patients of relapsed/refractory LCH.

Erdheim-Chester disease (ECD) is a rare histiocyte disorder characterized most commonly by distal symmetric osteosclerosis of the long bones and retroperitoneal soft tissue infiltration. However, the disease also frequently affects periorbital soft tissue and can cause cardiac, neurologic, and pulmonary dysfunction. The optimal therapy for ECD remains to be defined, though interferon is used frequently in the front-line setting (16). BRAF V600E mutations occur in approximately 50% of patients and can BRAF inhibitors such as vemurafenib are efficacious in the treatment of ECD but skin toxicity can be limiting (17). Recent evidence has implicated TNF-alpha in the pathogenesis of ECD (18).

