5.5 Criteria for Taking a Participant Off Protocol Therapy

Duration of therapy will depend on individual response, evidence of disease progression and tolerance. In the absence of treatment delays due to adverse event(s), treatment may continue for 12 cycles or until one of the following criteria applies:

- Disease progression
- Intercurrent illness that prevents further administration of treatment
- Unacceptable adverse event(s)
- Participant demonstrates an inability or unwillingness to comply with the oral medication regimen and/or documentation requirements

- Participant decides to withdraw from the protocol therapy
- General or specific changes in the participant's condition render the participant unacceptable for further treatment in the judgment of the treating investigator
- Recurrent toxicity (see section 6)
- Patient becomes pregnant or cannot comply with birth control requirements.

Participants will be removed from the protocol therapy when any of these criteria apply. The reason for removal from protocol therapy, and the date the participant was removed, must be documented in the case report form (CRF). Alternative care options will be discussed with the participant.

A QACT Treatment Ended/Off Study Form will be filled out when a participant is removed from protocol therapy. This form can be found on the QACT website or obtained from the QACT registration staff.

In the event of unusual or life-threatening complications, treating investigators must immediately notify the Overall PI, [name] at [contact] or [contact] ([name]).

5.6 **Duration of Follow Up**

Participants will be followed for 3 years from the initiation of treatment, until subsequent therapy or until removal from study or death, whichever occurs first. Participants removed from protocol therapy for unacceptable adverse event(s) will be followed until resolution or stabilization of the adverse event.

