5.7 Criteria for Taking a Participant Off Study

Participants will be removed from study when any of the following criteria apply:

- Lost to follow-up
- Withdrawal of consent for data submission
- Initiation of subsequent therapy
- Death
- Completion of all study procedures

The reason for taking a participant off study, and the date the participant was removed, must be documented in the case report form (CRF).

A QACT Treatment Ended/Off Study Form will be filled out when a participant comes off study. This form can be found on the QACT website or obtained from the QACT registration staff.

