11.1.4 Progression-Free and Overall Survival

Overall Survival: Overall Survival (OS) is defined as the time from randomization (or registration) to death due to any cause, or censored at date last known alive.

Progression-Free Survival: Progression-Free Survival (PFS) is defined as the time from randomization (or registration) to the earlier of progression or death due to any cause. Participants alive without disease progression are censored at date of last disease evaluation.

11.1.5 Response Review

Radiology will be centrally reviewed by the DF/HCC Tumor Imaging Metrics Core (TIMC) and the treating clinician will add clinical data (e.g., status of skin lesions not assessable by radiology) as appropriate.

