13.6 Analysis of Secondary Endpoints

Secondary endpoints are

- a) Duration of response defined as the time elapsing between the documentation of the onset of remission until clinical and/or radiographic evidence of progression.
- b) Progression-free survival (PFS), where time to event for PFS is the time from study enrollment until the time of first occurrence of new lesions, progressive disease, or death from any cause, or until last contact if no event occurs;
- c) Overall survival (OS), calculated as the time from enrollment until death or last contact; and,
- d) The proportion of participants reporting grades 3-4 toxicity, for each CTC v4 toxicity code
- e) Serial quantification of BRAF mutation in urine and plasma cell free DNA in patients with an identifiable BRAF mutation at baseline.
- f) Serial quantification of serum TNF-alpha levels in all patients, even if not elevated at baseline.

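### Follow-up stops at new therapy although overall survival is a secondary endpoint, and Section 13.6 does not match Section 11 on PFS censoring and duration of response

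*Combined protocol and SAP*

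**What the plan says.** **Follow-up.** Section 1 ends it at 36 months or when patients start another treatment: "until they initiate a new therapy for their underlying disease, whichever occurs first". Section 5.6 sets three years, "until subsequent therapy or until removal from study or death, whichever occurs first". Section 5.7 lists "Initiation of subsequent therapy" as a reason to leave the study, not only the study drug.

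**Overall survival.** Section 1.3 gives the objective "To define the overall survival (OS) after treatment with lenalidomide", and Section 13.1 lists OS as a secondary endpoint. Section 11.1.4 measures it from registration "to death due to any cause, or censored at date last known alive". In Section 13.6 it is "calculated as the time from enrollment until death or last contact". Neither definition says what happens at new therapy. Following patients for survival is mentioned only in Section 6, for blistering rash.

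**Other secondary endpoints.** For patients without an event, Section 11.1.4 censors PFS at the last disease evaluation and Section 13.6 at last contact. Duration of response ends at progression or death in Section 11.1.3. In Section 13.6 it ends at progression only, with no censoring rule. Section 13.6(d) reports toxicity of grades 3 and 4.

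**The concern.** An endpoint that counts every death needs vital status for every patient over the period reported. Here collection stops at an event that may itself be related to prognosis. If patients who change therapy have a different risk of death from those still followed, a survival estimate that censors them at the change is biased.

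The direction is open. OS would read too high if switchers are at higher risk than those who remain. It would read too low if the sickest die without switching, or if the later therapy works. Section 2.1 makes both plausible: it describes disseminated histiocytic sarcoma as "typically fatal within six months", and it says that "vemurafenib can be effective in cases of LCH that harbor the BRAF mutation".

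The mismatch between Sections 11 and 13.6 is a separate matter. No section says which governs, so two analysts who each follow the plan could report different PFS and duration of response from the same data.

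**Working it through.** **1. The plan's own figure.** Section 13.1 gives 90% exact limits of 7-53% for 3 responses in 12. Clopper-Pearson gives 7.2% to 52.7%, so the figure reproduces. For 2 in 12 the limits are 3.0% to 43.8%, which contain 5%, as stated. Nothing below touches this rule.

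**2. OS range without any hazard assumption.** Take 12 patients, d recorded deaths, k switchers of unknown status, and all others followed to the time point. The OS proportion then lies between (12 - k - d)/12 and (12 - d)/12, a width of k/12.

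- k = 1: 1/12 = 8.3 points. k = 3: 25 points. k = 6: 50 points.
- d = 2, k = 3: from 7/12 = 58.3% to 10/12 = 83.3%.

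For scale, the binomial standard error at 75% is sqrt(0.75 × 0.25/12) = 12.5 points.

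**3. Direction of bias (illustration only).** The documents give no hazards, no switching rate, no OS landmark and no named estimator. Assume a death hazard of 0.01 per month before new therapy, 30% to 70% of patients starting new therapy by month 36 in the absence of death, and a hazard ratio r afterwards. Kaplan-Meier OS censored at new therapy is about 70% at month 36 in every case, since exp(-0.36) = 0.698.

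| r | True 36-month OS | Bias (points) | Unrecorded deaths per 12 |
|---|---|---|---|
| 0.5 | 72-75% | -2 to -6 | 0.3-0.8 |
| 1 | 70% | 0 | 0.5-1.4 |
| 2 | 60-66% | +4 to +9 | 1.0-2.6 |
| 4 | 48-61% | +9 to +22 | 1.6-4.1 |

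The sign depends on r, which the documents do not give. If few switch, the bias nearly vanishes. With 10-30% of progressors switching (9-month median to progression, 80-month median survival after it, 0.3% per month death before it), the bias is +0.2 to +0.9 points, with 0.2-0.6 deaths unrecorded.

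**4. Duration of response.** Assume a 12-month median to progression and treat deaths as censored under Section 13.6. Section 2.1 reports 28-32% deaths over 4-6.5 years in adult LCH, so h lies between -ln(0.72)/78 = 0.0042 and -ln(0.68)/48 = 0.0080 per month. Counting death, the median is ln2/(ln2/12 + h) = 11.2 or 10.5 months, against 12.0 when it is not counted. Those death rates are a weak anchor, because they do not come from a relapsed or refractory mixed-histiocytosis cohort.

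**5. PFS.** Assessments after treatment are 3 months apart to month 24 and then 6 months apart to month 36. A patient still in contact but between assessments could therefore have censoring dates up to about 3 to 6 months apart. If scans and contact stop together, the two rules give the same result.

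The events are not clearly the same either. Section 13.6 counts any new lesion. The overall-response table in Section 11.1.2 classes new lesions at one site with regression at another as intermediate, and the nodal column in Section 11.1.2.1 requires more than 1.5 cm. Other parts of Section 11, such as the skin rules, do treat a new lesion as progression.

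**6. Grade 5.** A fatal toxicity outside the grade 3-4 proportion moves it by 1/12 = 8.3 points.

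**7. Removal for toxicity.** Section 5.6 also ends follow-up at removal from study.

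| Event | Section 6 | Off-study list, Section 5.7 |
|---|---|---|
| Blistering rash | Text: followed for survival. Table 3: removed from study | Not listed |
| Arterial thromboembolism | Text: removed from study | Not listed |
| Grade 4 non-blistering rash or neuropathy | Table 3: removed from study | Not listed |

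**The case against.** Both OS definitions provide for censoring, so censoring a switcher is within the definition. Deaths before new therapy are captured, and a last-known-alive date could admit later information. This stands against a reader who infers that OS cannot be measured at all. It does not supply the missing data: a censoring rule plans no contact, and status learned by chance would be incomplete and selective.

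A reader might also infer that OS will be overstated, because switchers have usually progressed. The documents do not support a sign, for the reasons given under the concern. Nor do they show that the loss is irreparable, since a record check could recover vital status where consent allows. The consent form is not in the text reviewed.

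The simulated biases rest on invented inputs. That is correct, and the conclusion does not use them. A PFS effect requires contact to continue after imaging; the calendar largely pairs the two, and ordinary dropout gives no difference.

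Most of the toxicity-removal wording may be loose usage for stopping treatment. Section 10 speaks in the same way of removal for progressive disease, which Section 5.5 treats as a reason to stop therapy and Section 5.7 does not list. Section 5.5 also treats unacceptable adverse events as reasons to stop therapy. That reading is likely, and only the blistering-rash passages clearly conflict, but Section 5.6 makes follow-up depend on the word.

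Grade 5 events still reach adverse event forms, serious adverse event reports and the safety committee (Sections 7.3, 7.5 and 13.4). The gap is only in the analysis definition, and it is minor.

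Finally, this is a 12-patient pilot with a descriptive OS endpoint and no test. That limits the consequence, but each missing status then weighs more.

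**Conclusion.** The point holds and should be fixed. As written, deaths after new therapy are not planned to be collected, and OS censoring at that point is potentially informative in an unknown direction. The firm size is 8.3 points of possible OS range per switcher of unknown status. It assumes 12 patients, with all others followed to the time point. Any Kaplan-Meier bias is illustrative and may be near zero.

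The conflicts between Sections 13.6 and 11 on PFS censoring and duration-of-response events are plain in the current text. Consistency on new lesions is doubtful. The effect on PFS is conditional; the effect on duration of response is about 1 to 1.5 months of median under the stated assumptions. The primary endpoint and the 3-of-12 rule do not change.

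**What to change.** - **Sections 1, 5.6 and 5.7:** end disease assessments at new therapy, but keep collecting survival status by record check or call to month 36 for all treated patients who have not withdrawn consent. Confirm that the consent form covers this.
- **Section 13.6:** adopt the PFS censoring rule of Section 11.1.4 and the duration-of-response events and censoring of Section 11.1.3. Refer to one definition of progression for new lesions. Report toxicity of grade 3 or higher (3-5).
- **Section 6 with Sections 5.6 and 5.7:** state whether removal from study ends follow-up or only treatment, and reconcile the two blistering-rash passages.

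The cost is amendment wording, possibly consent wording, and a status check for at most 12 patients, with no added scans or procedures.

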1.1 Study Design

This is a single agent, phase II open-label study of single agent lenalidomide in patients with relapsed/refractory ECD, LCH, or HS.

1.2 Primary Objectives

To estimate the response rate of patients with relapsed/refractory ECD, LCH, and HS with single agent lenalidomide.

1.3 Secondary Objectives

- To define the progression free survival (PFS) after treatment with lenalidomide
- To define the overall survival (OS) after treatment with lenalidomide
- To describe the safety profile of lenalidomide in LCH, ECD, and HS
- To assess quantitative changes in urinary and plasma cell free DNA harboring the BRAF V600E mutation and correlate the presence or absence of the BRAF V600E mutation with response
- To assess serial changes in TNF-alpha levels in patients treated with lenalidomide
- To assess the mutational landscape of these diseases using Oncopanel

2. BACKGROUND

2.1 Study Disease(s)

Langerhans Cell Histiocytosis (LCH) is a rare disease (1-10 cases per million) of unknown etiology distinguished by the clonal proliferation of pathologic histiocytes derived from bone marrow dendritic cells (1). BRAF mutations have been identified in approximately 50% of cases but the inciting event remains unclear (2). Clinical manifestations are related to the pattern of infiltration or organ involvement which is heterogeneous, can involve single or multiple organs, and can be associated with varying, often unpredictable outcomes ranging from spontaneous regression to multiple episodes of reactivation, long term debilitating sequelae, rapid progression, and death.

The natural history of LCH is ill defined in adults. Studies of disease outcomes have been primarily undertaken in the pediatric population [3]. Assessments of adult patients with LCH have reported death events in 28-32% of patients with 4-6.5 year follow up [4,5]. There is no agreed standard of care in adults for either first-line or reactivation disease. As such, there is an unmet need for a well-tolerated, efficacious agent to treat adult LCH.

A recently completed international adult study (LCH-A1) attempted to define and implement a uniform treatment approach in adults with respect to smoking cessation and the use of prednisone, vinblastine, and 6-mercaptopurine. Although final analysis of the data have not been completed at the present time, preliminary analysis indicates that many adult patients were unable to tolerate the standard pediatric multi-agent regimen of prednisone and vinblastine, due to neuropathy attributable to the latter agent. This was corroborated at Baylor College of Medicine where a study of vinblastine in LCH was terminated early when 5 or the first 7 adults treated developed Grade 3-4 toxicity at some point during therapy, and only 2/7 patients were able to complete the treatment course as prescribed by the protocol. Within a median of 6 months after starting therapy, 3/6 patients were in remission and 3/6 had active disease [6].

Reported disease reactivation rates after frontline therapy in adults vary widely. Multisystem LCH reactivation has been reported in 26-43% of patients [4, 7, 8] treated with a variety of

steroid and cytotoxic regimens. Nucleoside analogues such as cladribine and cytarabine have proven to be effective in this setting but are not without issue. Cytarabine can have significant hematologic toxicity (9). Cladribine cannot be administered for longer than six months due to concerns about secondary myelodysplasia (MDS) while studies have suggested that outcomes are better when LCH is treated with a given agent for at least 12 months (10,11). Clofarabine has proven to be effective in patients with cladribine and cytarabine-resistant disease, but causes significant hematologic and hepatic toxicity as well as cause hand-foot syndrome (12). The BRAF inhibitor vemurafenib can be effective in cases of LCH that harbor the BRAF mutation but there are significant concerns about the potential for secondary skin cancers (13). Monitoring of BRAF mutational burden in cell free DNA may be a useful marker for disease progession in this patient population, however (14).

Histiocytic sarcoma is an aggressive neoplasm deriving from non-Langerhans dendritic cells. When localized, surgery and/or radiation can be effective. However, disseminated HS responds poorly to chemotherapy and is typically fatal within six months (15). Therefore, new therapies are required for all patients with multifocal HS and for patients of relapsed/refractory LCH.

Erdheim-Chester disease (ECD) is a rare histiocyte disorder characterized most commonly by distal symmetric osteosclerosis of the long bones and retroperitoneal soft tissue infiltration. However, the disease also frequently affects periorbital soft tissue and can cause cardiac, neurologic, and pulmonary dysfunction. The optimal therapy for ECD remains to be defined, though interferon is used frequently in the front-line setting (16). BRAF V600E mutations occur in approximately 50% of patients and can BRAF inhibitors such as vemurafenib are efficacious in the treatment of ECD but skin toxicity can be limiting (17). Recent evidence has implicated TNF-alpha in the pathogenesis of ECD (18).

TNF-alpha is thought to promote the proliferation and survival of dendritic cells and histiocytes and thalidomide inhibits TNF-alpha production by affecting the gene promoter as well as other anti-cytokine effects (19). Thalidomide has reported activity in histiocyte disorders, including HS and LCH. Thalidomide has several drawbacks, including the common side effects of neuropathy and somnolence. Lenalidomide is potentially a more potent TNF-alpha inhibitor and does not cause neuropathy, making it potentially a more useful agent for prolonged administration. There are case reports describing the activity of lenalidomide in a variety of histiocyte disorders (20, 21). There is also emerging evidence on the important role of activation of RAS-PI3K-AKT signaling in histiocyte disorders and the AKT inhibitor afuresertib has been studied in LCH patients (22, 23). Lenalidomide potentially has inhibitory effects on AKT as well (24). We therefore planned a broader study to more systematically evaluate the efficacy of lenalidomide and describe the toxicity of lenalidomide in a population of patients with LCH and HS. Given the putative mechanism of action we seek to correlate serum TNF-alpha levels with response. In patients with a known BRAF V600E mutation we also wish to explore the possibility of using BRAF mutation burden assessed in urine and plasma cell free DNA as a biomarker of disease activity.

